7. STUDY PROCEDURES

The study schedule of events and the specific procedures performed at each visit are shown in Table 1, Schedule of Events. Each patient will undergo a total of 9 visits, including an initial/screening visit, the procedure visit, and 7 post-operative visits. More visits may be required when medically necessary.

Table 1: Schedule of Study Events

Procedures	Screening ^a	Procedure Date	W 1 ^c	M 1 ^e	M 3 ^{g,h,i}	M 6, 12, 18, 24 or W/D ^{g,h,i}
Informed Consent	X					
Inclusion/Exclusion	X					
Demographics	X					
Targeted Medical History	X					
Karnofsky Performance	X			X	X	X
Pertinent Medication	X		X	X		
Discontinue anticoagulation, as clinically indicated	X	X				
Imaging Scan	X ^f		X ^d	X ^f	X ^f	X ^f
Record index tumor characteristics	X					
Cryoablation procedure		X ^b				
Labs	X					
Quality of Life (SF-12)	X			X	X	
Safety Assessment		X	X	X	X	X

^a All screening visit requirements should be within 8 weeks of the initial cryoablation procedure. Any items (e.g., imaging or lab assessment) previously conducted as routine standard of care prior to the signed informed consent may be used to satisfy the screening requirements provided they are completed within 8 weeks of the initial cryoablation procedure.

^b If multiple tumors are planned for study inclusion, treatment of all study index tumors should be completed within an 8 week window.

^c The week 1 follow up visit may take place prior to discharge from the hospital or within 1 week (7 days) of the cryoablation procedure.

^d Week 1 imaging may be a chest CT ± contrast or chest X-Ray

^e Month 1 visit window 30 days -7/+21 days

^f Chest CT scan ± contrast (contrast is preferred)

^g Months 3, 6, 12, 18 and 24 visit window +/- 30 days

^h In the event of multiple cryoablation procedure dates, the most recent procedure date will serve as the reference for determining the follow up visit window.

ⁱ While return visits are preferred to be conducted in the clinic setting, in the event the patient is not able to return due to distance or illness, follow up assessments (i.e. all assessments with the exception of imaging) may be conducted via telephone or tele-video (e.g. Skype). Tele-video should only be considered if the patient has the knowledge and access to such technology.

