7.8. Repeat Cryoablation Treatment(s) or Alternative Additional Treatment

Patients may receive additional cryoablation treatment(s) to the index tumor(s) initially subjected to cryoablation while participating in the study protocol. This additional cryoablation may be performed on the index tumor(s) provided that the additional treatment is performed with Galil Medical technology. In this situation, for each index lesion retreated, follow-up visits will restart per the study protocol and continue through the 24 month visit after the date of the repeat cryoablation treatment. When possible, if multiple tumors are present, all efforts should be made to align all follow up visits. For any index lesion not subjected to retreatment, the data collection continues per protocol.

- Baseline labs are recommended to be repeated prior to any repeat cryoablation procedure;
- It is recommended to discontinue anticoagulation as clinically indicated;

- SF-12 will not be collected prior to or after any repeat cryoablation of index tumor(s);
- Pertinent medications should be reviewed prior to and after any repeat cryoablation of index tumor(s);
- All other follow-up requirements are still applicable.

If other local treatment (e.g. radiofrequency ablation, microwave ablation, surgery, radiation) is used on the index tumor(s) initially treated, then the patient must be withdrawn from the study.

Data will be collected regarding any systemic cancer therapy the patients receive during the course of the study.

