8.7. Response Determination

The month 1 post-ablation CT examination will be used as the reference for determining index ablation zone response at each follow up interval after cryoablation. Sequential follow up intervals will be used to determine local failure.

In the unforeseen circumstance where the patient is unable to complete imaging according to the month 1 follow up visit, the month 3 imaging study may serve as the reference for determining index tumor response at each follow up interval after cryoablation. Every effort should be made to comply with the month 1 imaging requirement.

Efficacy at 12 months post cryoablation will be based on local tumor control that will be separately assessed for each index tumor according to criteria below. Each ablation zone will be evaluated at each time point by measuring its 3 axes (longest diameter and the two perpendicular diameters). For each ablation zone individually, the sum of these three measures will be compared to the 1 month baseline for tumor response and the previous follow up interval imaging study for local failure.

Each ablation zone measurement assessment, along with the overall clinical evaluation of the patient, will be evaluated by an independent imaging panel to assess the final response determinations. This final review can be used in the analysis in the event of 'indeterminate' imaging measurement assessments.

Local Tumor Control will be defined as the absence of local failure.

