8.7.4 Local Failure

Local failure will be defined as $\geq 20\%$ increase in the sum of the three axes of measurements (longest diameter plus the two perpendicular diameters) when compared with the nadir of this 3 axes measurement.

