10.5.3. Primary Endpoint

The primary endpoint for this study is defined as follows: efficacy of cryoablation on local tumor control for each index tumor in patients with pulmonary metastatic disease at 12 months post cryoablation.

Patients are allowed up to 6 tumors and the primary efficacy endpoint (tumor control) will be calculated on a per tumor level. To be considered a success each tumor treated during the baseline procedure must meet the tumor control criteria at the 12 month follow-up visit.

The local tumor control counts and rates will be presented along with the 95% two-sided confidence intervals for the rates. The rate numerator will be defined as the number of tumors experiencing tumor control at 12-months. The rate denominator will be defined as the total number of tumors evaluated at 12-months.

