For the formal primary endpoint hypothesis test, patients with missing 12-month tumor evaluations will be imputed using multiple imputation (SAS PROC MI using FCS logistic regression and including tumor status at prior visits), except in the following case where previous visit evidence can be used to impute 12-month status:

- Subjects with local tumor failure at 6-months will be considered a local tumor failure at 12-months post-index procedure.

Additional sensitivity analyses to be conducted:

- Worst case: all missing data are imputed to be failures
- Best case: all missing data are imputed to be successes
- Complete case: all missing data are treated as missing and not imputed

Subset Analyses

Analysis will be done on outcomes for subgroups including, but not limited to, gender and lesion size. Additional non-protocol defined subgroups include: number of needles used, number of lesions, primary cancer diagnosis, and lesion location.

Poolability Analyses

A poolability analysis among investigational centers and geographies (US/OUS) will be performed for the primary efficacy endpoint. This analysis will be performed on the ITT population.

Poolability of Sites

Combining of Small Sites

Sites contributing less than 5 subjects to the as treated analysis set will be considered “small sites” and ordered by the date of first enrollment in the as treated analysis set. Starting with the first “small site”, a pseudo-site will be created by adding subjects from successive “small sites”. If the number of subjects reaches or exceeds the size of the median enrollment of the “large sites”, then a second pseudo-site will be created. Additional pseudo-sites, if needed, would be created in the same manner.

Primary Endpoint by Site

Among sites and pseudo-sites, the proportions of subjects who achieve local tumor control at 12 months will be compared using logistic regression. If the resulting p-value is ≤ 0.05 , further exploratory analysis will attempt to identify covariates (baseline characteristics) that may explain differences among the sites. Otherwise, the data will be considered to be poolable across study sites.

Poolability of Geographies

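### The SAP's formal primary test treats only month-6 local failures as known, so a failure recorded at another time before withdrawal can be imputed as controlled, and the scoring of re-cryoablated tumours is unstated

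*SAP*

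**What the plan says.** **Definition.** Protocol 8.7: "Local Tumor Control will be defined as the absence of local failure". Section 8.7.4 sets failure at a 20% or greater rise in the three-axis sum "when compared with the nadir of this 3 axes measurement". Protocol 10.5.3 adds that "each tumor treated during the baseline procedure must meet the tumor control criteria at the 12 month follow-up visit", and its denominator is the tumours evaluated at 12 months.

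**Missing month-12 status.** The SAP (Handling of Missing Data) uses multiple imputation for the formal test: "SAS PROC MI using FCS logistic regression and including tumor status at prior visits". Its one exception is "Subjects with local tumor failure at 6-months will be considered a local tumor failure at 12-months post-index procedure". Worst-case, best-case and complete-case analyses are planned as sensitivity analyses.

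**When failure can be recorded.** Local recurrence at the index tumour is assessed from month 1 onwards (protocol 7.5 to 7.7), so it can be recorded at month 3. Protocol 7.9 asks patients who terminate early to have a final chest CT. No protocol CT falls between months 6 and 12.

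**What follows a failure.** Under protocol 7.8, if other local treatment "is used on the index tumor(s) initially treated, then the patient must be withdrawn from the study". Repeat cryoablation with the sponsor's system is allowed, and "for each index lesion retreated, follow-up visits will restart per the study protocol and continue through the 24 month visit". The SAP analyses re-cryoablated tumours in a supportive summary at 12 months after retreatment.

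**The concern.** Local control is the only hypothesis-tested endpoint and is compared with a fixed 84% goal, so how a few tumours are scored can decide the result. Three gaps arise.

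1. **Known failures that are imputed.** A tumour that fails at month 3, or on an unscheduled or exit scan, and is then treated by another local method has no month-12 evaluation. Its outcome is known, but the SAP treats it as missing. Earlier status in the imputation model makes imputed control less likely without ruling it out. A failure seen only on an unscheduled scan may not enter the model at all.
2. **Wrong unit.** The carry-forward rule speaks of subjects, although the endpoint is per tumour and a patient may have up to 6. Read literally, one failed tumour could also fix as failures the patient's other tumours with missing month-12 status.
3. **Re-cryoablated tumours with a later scan.** Neither document says whether the earlier failure stands in the primary test, or which month-12 visit counts once the schedule restarts.

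Separately, the protocol 10.5.3 denominator leaves withdrawn tumours out, while the SAP imputes them.

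**Working it through.** **Inputs.** Protocol 10.1 and SAP Sample Size Justification: n = 203 tumours, reject if R ≥ 181, null rate 0.84, planned rate 0.91, stated alpha 0.0239, stated power 0.8501, and 226 tumours after 10% attrition. The documents give no count of early failures, withdrawals for other local therapy, or retreatments, so every count below is an assumption. The exact rule with independent tumours stands in for the SAP's random-effects model with a Wald bound. Between-imputation variance is ignored.

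**1. The plan's own figures.** With P(R ≥ r | n, p) = Σ C(n,i) pⁱ(1−p)ⁿ⁻ⁱ over i = r to n:
- P(R ≥ 181 | 203, 0.84) = 0.0239
- P(R ≥ 181 | 203, 0.91) = 0.850
- 203 / 0.90 = 225.6, rounded up to 226

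All reproduce. The exact one-sided 97.5% lower bound is 0.8405 at 181 of 203 and 0.8349 at 180 of 203, so one tumour can separate success from failure.

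**2. Shifted thresholds.** If k true failures are counted as controlled, the goal is met when true successes reach 181 − k. At true control of 0.84:

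| k | P(R ≥ 181 − k) |
|---|---|
| 0 | 0.0239 |
| 1 | 0.0384 |
| 2 | 0.0592 |
| 3 | 0.0875 |
| 4 | 0.1244 |

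The rows k = 1 to 4 apply directly to re-cryoablated tumours only if those tumours are read as controlled.

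**3. Recorded failures that are imputed.** With m such tumours, each drawn as controlled with probability q, the rate is Σ C(m,j) qʲ(1−q)ᵐ⁻ʲ × P(R ≥ 181 − j) over j = 0 to m.
- m = 1, q = 0.10: 0.9 × 0.0239 + 0.1 × 0.0384 = 0.025
- m = 2, q = 0.10: 0.81 × 0.0239 + 0.18 × 0.0384 + 0.01 × 0.0592 = 0.027
- m = 3, q = 0.10: 0.729 × 0.0239 + 0.243 × 0.0384 + 0.027 × 0.0592 + 0.001 × 0.0875 = 0.028
- m = 3, q = 0.25: 0.4219 × 0.0239 + 0.4219 × 0.0384 + 0.1406 × 0.0592 + 0.0156 × 0.0875 = 0.036

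**4. Protocol 10.5.3 denominator (not the SAP test).** Leaving out 1, 2, 3 or 4 failures gives exact cut-offs of 181/202, 180/201, 179/200 and 178/199. The corresponding rates are 0.024, 0.038, 0.059 and 0.088.

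**5. Which reading the text favours for a re-cryoablated tumour.**
- *For failure:* control means absence of local failure (protocol 8.7), success attaches to tumours treated at the baseline procedure (10.5.3), the SAP carry-forward rule counts from the index procedure, and retreated tumours have their own supportive outcome.
- *For control:* 10.5.3 judges status at the month-12 visit, visits restart after retreatment, and the SAP thought it necessary to write an express rule for month-6 failures.
- *Undetermined:* no passage resets the nadir in 8.7.4, so an enlarged re-ablation zone could itself be read as failure.

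**The case against.** The strongest reply is that the plan already contains most of the answer. Month-6 failures are fixed. The imputation model uses earlier tumour status, so a month-3 failure would probably often be imputed as a failure. Table 1 lists withdrawal with the scheduled visits, so an exit scan may count as a prior visit. Available data on dropouts are to be included where possible, and the worst-case analysis scores every missing tumour as a failure. Ignoring between-imputation variance overstates the risk in step 3, because that variance widens the interval.

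Much of this stands and is why the imputation effect is put as small. It does not close the gap. The exception names one time point, so the formal test can still draw a recorded failure as controlled. The worst-case analysis does not alter that test, and it does not reach a re-cryoablated tumour with an observed scan.

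Three stronger readings are tempting but unsupported:
- **That the primary test drops these tumours.** It imputes them. Omission belongs to the protocol 10.5.3 denominator and the SAP's complete-case sensitivity analysis.
- **That re-cryoablated tumours will count as controlled.** The passages in step 5 lean the other way; the defect is that none says so.
- **That every ambiguity favours the device.** The literal subject-level reading would turn a patient's other tumours with missing status into failures and lower the rate.

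**Conclusion.** The point holds in a limited form and should be fixed. A stated rule in the SAP's formal test can give a wrong result for a tumour whose failure is already recorded. The likely size is small: 0.025 to 0.028 against a nominal 0.024 for 1 to 3 tumours at a 10% chance of imputed control, and 0.036 for 3 tumours at 25%.

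The re-cryoablation question is a genuine ambiguity. Its figures, 0.038 to 0.124 for 1 to 4 tumours, apply only under the reading the text favours less. They are not an estimate of the trial's actual error rate.

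The gap in the wording is certain. Its numerical effect rests on assumed counts, independent tumours and the exact-rule approximation, so confidence in the size is moderate at best.

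**What to change.** Analysis wording only. Visits, scans, and the withdrawal and retreatment rules stay as they are.

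1. **SAP, Handling of Missing Data.** Make the rule apply to index tumours with local failure at any earlier assessment, including unscheduled or exit scans. Impute only tumours with no recorded failure.
2. **SAP primary endpoint and protocol 10.5.3.** State that an index tumour re-cryoablated or given other local therapy after a local failure is a primary failure, for events up to the month-12 visit scheduled from the initial treatment course. For staged treatment, Table 1 note h says "the most recent procedure date will serve as the reference for determining the follow up visit window"; say explicitly that retreatment does not restart this clock for the primary endpoint. With 8-week staging and the +30-day window, that visit can fall 365 + 56 + 30 = 451 days after the first-treated tumour's ablation. A cut-off at 12 months from each tumour's own ablation would miss failures first seen there.
3. **One determination of failure.** Use the final determination after central review (protocol 8.7 and 16.2) throughout. Protocol 7.8 does not make failure a condition of repeat cryoablation, so also add a sensitivity analysis that counts investigator-determined failures.
4. **Alignment and reporting.** Bring the 10.5.3 denominator into line with the SAP, keep post-retreatment control as supportive, and report the number of rescued tumours by route.

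**Cost.** The reported rate may be slightly lower. If the planned 91% included rescued tumours, power falls below 85%. If they make up 0.5 percentage points (about 1 of 203), P(R ≥ 181 | 203, 0.905) = 0.78; if 1 point (about 2 of 203), P(R ≥ 181 | 203, 0.90) = 0.70. The change makes month-12 status explicitly cumulative, so record it as a dated endpoint clarification.

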The primary efficacy endpoint for the trial is 12-month local control. The papers shown below were used as reference for clinicians who determined a clinically relevant efficacy endpoint performance goal was 84% success at 12-months. This observed cryoablation group's local control rate will be tested against this performance goal.

Paper	Lesions	12-month Local Control Success	Lower 97.5% 1-sided Wilson CI
Okuneiff (2006)	125	91%	0.8469
Rusthoven (2009)	63	100%	0.9425
Baschnagel (2013)	47	97%	0.8757
Ricardi (2012)	77	94%	0.8632
Norihisa (2008)	43	94.50%	0.8337
Yoon (2006)	101	90%	0.8261

This test is accomplished by testing against the following hypotheses:

$$H_0: C_{\text{DEVICE}} \leq 84.0\%$$

$$H_a: C_{\text{DEVICE}} > 84.0\%$$

where C_{DEVICE} is the observed cryoablation local control rate at 12-months.

The null hypothesis will be rejected and the primary efficacy endpoint performance goal will be met if the lower bound of the one-sided 97.5% confidence interval for the 12-month tumor local control rate is greater than 84.0%.

PASS 12 was used to calculate the sample size needed. A sample size of 203 lesions achieves 85% power (and guarantees at least 80% power) to detect a difference ($P_1 - P_0$) of 0.0700 using a one-sided binomial test. The target significance level is 0.0250. The actual significance level achieved by this test is 0.0239. These results assume that the population proportion under the null hypothesis is 0.8400.

Power Analysis of One Proportion

Numeric Results for testing $H_0: P = P_0$ versus $H_1: P > P_0$

Test Statistic: Exact Test

Power	N	Proportion		Target Alpha	Actual Alpha	Beta	Reject H_0 If $R \geq$ This
		Given H_0 (P_0)	Given H_1 (P_1)				
0.8501	203	0.8400	0.9100	0.0250	0.0239	0.1499	181

To account for up-to a 10% 12-month lesion attrition rate, the final sample size has been increased to 226 lesions.

Note that, for the purposes for sample size calculations, the observations are assumed to be independent. However, the primary analyses will account for within subject correlation, as described below.

General Analysis Methods

Data will be analyzed using descriptive statistics. Continuous variables (e.g., age) will be summarized by the number of patients, mean, standard deviation, median, interquartile range, minimum and maximum. Categorical variables (e.g., race) will be summarized by frequencies and percentages of patients in each category. 95% confidence intervals will be calculated as appropriate.

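### Read literally, the SAP's best-case and complete-case analyses reverse or drop documented month-6 failures, so two of the three sensitivity analyses are biased upward

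*SAP*

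**What the plan says.** The SAP section Handling of Missing Data sets the rule for the formal primary test. Absent month-12 evaluations are multiply imputed, "except in the following case where previous visit evidence can be used to impute 12-month status". One case is listed: local failure at month 6 counts as local failure at month 12.

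Three additional sensitivity analyses follow. The worst case scores missing data as failures. The other two read "Best case: all missing data are imputed to be successes" and "Complete case: all missing data are treated as missing and not imputed". None of the three mentions the month-6 exception. The SAP section Analysis Populations describes the sensitivity analyses as using a different imputation from the primary analysis, and the revision history lists the two sets of imputations as separate additions.

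Three protocol sections bear on this:

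- Section 8.7 defines local tumour control as no local failure.
- Section 7.8 says that if another local treatment "is used on the index tumor(s) initially treated, then the patient must be withdrawn from the study". It also restarts the visit schedule of an index tumour that is re-cryoablated.
- Section 10.5.3 takes as the rate denominator the tumours evaluated at 12 months.

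**The concern.** A month-6 failure is an observed outcome. The SAP treats it that way in the primary test, but it words the rule as an exception within that test's imputation scheme. A programmer who follows the sensitivity list as written would find the tumour's month-12 field empty. The tumour would then become a success in the best case and disappear from the complete case.

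The affected tumours are not a random subset. Failure can lead to other local treatment and withdrawal, or to re-cryoablation and a new visit clock, so a failed tumour can plausibly be the one without a month-12 reading. The sensitivity analyses are meant to show how far missing data could move the primary result. If two of them rise because known failures were removed or reversed, their agreement with the primary result says little about data that are really missing.

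**Working it through.** **The plan's own design figures.** The null value comes from SAP, Sample Size Justification: "These results assume that the population proportion under the null hypothesis is 0.8400". The same section puts the alternative 0.07 higher, at 0.91, with a one-sided exact test, a nominal level of 0.025 and an attained level of 0.0239. With n = 203 and rejection at 181 or more controlled tumours, the exact binomial gives:

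- P(X ≥ 181 | 0.84) = 0.0239. A cut-off of 180 would give 0.0384, so 181 is right.
- P(X ≥ 181 | 0.91) = 0.8501.
- 203 / 0.90 = 225.6, rounded up to 226.

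All of these match the SAP.

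**Set-up.** Take N = 226 and true control at the goal, 84%. That is about 190 controlled and 36 failed tumours. Let q be the share of all failures that are both known at month 6 and without a month-12 evaluation. The documents give no value for q, so it is an assumption and is varied. Month-6 failures that do have a month-12 evaluation are not missing and are not affected. At first, nothing else is missing.

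**Formulas, as a proportion of all tumours.**

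- Complete case, as written: 0.84 / (1 − 0.16q)
- Best case, as written: 0.84 + 0.16q
- Either analysis with the month-6 rule applied: 0.84

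| q | Share of tumours affected (0.16q) | Complete case | Best case | Rule applied |
|---|---|---|---|---|
| 10% | 1.6% | 0.84/0.984 = 85.4% | 85.6% | 84% |
| 25% | 4.0% | 0.84/0.96 = 87.5% | 88.0% | 84% |
| 50% | 8.0% | 0.84/0.92 = 91.3% | 92.0% | 84% |

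In whole tumours at q = 50%, 18 failures are affected. The complete case is 190/(226 − 18) = 190/208 = 91.3%, the best case is (190 + 18)/226 = 208/226 = 92.0%, and the true figure is 190/226 = 84.1%. The 18 tumours are 8.0% of 226, within the planned 10% attrition. That allowance is used up at q = 0.10/0.16 = 62.5%, with no room left for death or other loss.

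**With other missing data.** Let 23 tumours (10%) be missing, k of them known month-6 failures and the rest a random draw from the remaining tumours. For k from 5 to 23:

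| | Complete case | Best case |
|---|---|---|
| As written | 86.0–93.6% | 87.4–94.2% |
| Month-6 rule applied | 83.8–84.1% | 84.1–85.2% |

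The corrected complete case can fall about 0.3 points below 84.1%, because it keeps known failures but drops some controlled tumours with no reading.

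**The case against.** The SAP never says that the month-6 rule is switched off in the sensitivity analyses. It says such tumours will be considered failures at month 12, which can be read as assigning a status, so that they are no longer missing. It also promises to use available data from patients who drop out where possible. This stands as a possible reading. The limitation to the formal test, the word impute and the separate sensitivity list point the other way. Two analysts could produce different tables from the same text, so a clarification is needed under either reading.

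A best case is optimistic by design and cannot fall below the primary result. That is true, but it should bound what is unknown and not overturn what was recorded.

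The frequency of the problem is uncertain. Withdrawal is required only for other local treatment of an index tumour. A tumour re-cryoablated near month 6 would have its new month-6 CT near the original month 12, so imaging need not be absent. A tumour that fails at month 3 and leaves before month 6 falls outside the rule even in the primary test, so its loss cannot be put down to the rule's scope. These points stand, and they are why q is shown as a range.

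Two stronger readings are tempting:

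- A reader might infer that the trial's false-positive risk is inflated. Simulating independent tumours at a true 84%, the exact one-sided 97.5% lower bound exceeds 84% in about 26% (complete case) and 38% (best case) of trials at q = 25%, against 2.3% with the rule applied. The documents do not support that inference. No pass rule is attached to these analyses, the formal test keeps the month-6 rule, and the exact bound is only a stand-in for the random-effects Wald bound that the SAP specifies for the primary test.
- A reader might take 91–92% as the expected result for a device at the goal. It is one scenario, in which half of all failures are known at month 6 and unread at month 12.

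**Conclusion.** The point holds as a defect in two of the three sensitivity analyses under the literal text. The bias is upward. At a true 84% it runs from about 1.4 / 1.6 percentage points (complete / best case) at q = 10% to about 7.3 / 8.0 points at q = 50%. These figures assume 226 tumours, no other missing data and an assumed q. The direction does not depend on q, only the size does. The pass/fail decision is not at risk, and the worst case already scores these tumours as failures. What is lost is the ability of the best and complete cases to show the effect of data that are really missing.

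**What to change.** Add to the SAP's sensitivity section that the documented-failure rule of the primary analysis applies in every sensitivity analysis, and that best, worst and complete case act only on tumours whose month-12 status is still unknown after that rule. Define the complete case as tumours with a month-12 evaluation or a carried-forward failure.

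Keep the rule identical throughout. If it is widened to any local failure recorded before month 12, widen it in the primary analysis as well. Otherwise the analyses would differ in endpoint and not only in the handling of missing data.

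The cost is a short text change. The complete-case and best-case rates become less favourable. The complete-case denominator will also differ from the one in protocol section 10.5.3, and the SAP should note this.
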